### **Statistical Analysis**

The data will be analyzed using Statview version 5.0.1 will be used for statistical analysis. Power, the probability of rejecting a false null hypothesis, is fixed at 0.90. Two-sided significance level is set at 0.05. The sample size required for an attrition rate of 30% is therefore 40 subjects to be randomized into 2 groups of 20 each. A two way-repeated measures ANOVA will be used with main factors of prosthetic used and repeated testing session.

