More recently, technology has been used to assist with return to function in the amputee population. Microprocessor (MP) controlled knees are among the technological innovations applied to prostheses to not only return amputees to a basic function, but also with a view to return them to their highest possible function. Over the years, clinical use has shown that traditional knees provide the ability to complete ADLs and basic functions like sit – stand. However, activities like negotiating stairs/steps, walking on uneven ground and self-correction during tripping; functions which reintegrate amputees into unlimited community ambulation and social reintegration require prosthetics which advanced functionality. The Otto Bock C-leg is a MP knee that allows the patient a greater level of control in swing and stance phases of gait. This enables the TF amputee to adjust the requirements of gait during dynamic walking like changing the speed of walking, going up and down stairs and inclines, walking on grass and uneven surfaces and crossing an obstacle. The C-leg has been traditionally given to patients who begin post-amputation rehabilitation at a higher level, but are more expensive than traditionally mechanical knees. In the contrary however, a European study that defined health outcomes in terms of quality-adjusted life year (QALY), indicated that the C-leg showed a QALY gain of €3218 per patient (Brodtkorb et al 2008), makes it still financial viable keeping it mind its price tag.. The purpose of this study is to compare the traditional mechanical knee to the microprocessor knee (C-leg) in the dysvascular population. The study will specifically evaluate the potential of microprocessor knees to improve the quality of life in dysvascular transfemoral amputees. This includes identifying if the Cleg can increase the activity level to be classified at a higher level by the Medicare classification from K2 (lower level ambulators) to K3 (more proficient ambulators), along with increasing their social interaction in the community.

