# 3) Hypotheses & Research Objectives and Purpose:

Central Hypothesis: We hypothesize that giving microprocessor knees (C-leg®), will significantly increase everyday function, social interaction, and quality of life in K2 Dysvascular subjects with transfemoral amputation in comparison to a standard mechanical knee (both FDA Class II exempt devices). The study will primarily aim to study the impact of the C-leg on ADLs and community interaction ADLs and function:

Hypothesis 1: We hypothesize that the C-leg will significantly increase every day physical activity measured using GPS tracked activity in K2 Dysvascular subjects in comparison to a mechanical knee.

Hypothesis 2: We hypothesize that the C-leg will significantly increase functional mobility in K2 Dysvascular subjects compared to a mechanical knee: increased stepping measured using Step Activity Monitor (SAM), increased gait speed and distance measured by Six Minute Walk Test (6MWT), increased mobility measured by the Amputee Mobility Predictor (AMP).

Hypothesis 3: We hypothesize that the C-leg will significantly increase community mobility measured using GPS technology in K2 Dysvascular subjects in comparison to a mechanical knee.

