# Sub -hypothesis

- 3a: That C-leg will improve ambulation distance vs. mechanical knee
- 3b: That C-leg will improve time out of home vs. mechanical knee
- 3c: That C-leg will improve ability to use public transport vs. mechanical knee
- 3d: That C-leg will decrease gait aid vs. mechanical knee

Hypothesis 4: We hypothesize that the C-leg will significantly improve social integration as measured by CPI (Community Participation Indicators) in K2 Dysvascular subjects in comparison to mechanical knee.

Hypothesis 5: We hypothesize that the C-leg will significantly improve both static and dynamic balance as measured by Single Leg Stance (SLS), Timed Up and Go (TUG), BERG Balance Scale (BBS), Four Square Step test (FSST) and Dual task TUG tests in K2 Dysvascular subjects compared to a mechanical knee.

Hypothesis 6: We hypothesize that the C-leg will significantly improve self-reported measures in K2 Dysvascular subjects in comparison to mechanical knee.reduced falls measured by The Falls Efficacy Scale (FES), improved prosthesis use measured by The Prosthesis Evaluation Questionnaire (PEQ)

This study will be conducted at the Rehabilitation Institute of Chicago, [name].

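### Six hypotheses over about 16 outcomes have no primary outcome and no rule for when the central hypothesis is supported, so that claim has no defined error rate

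*Combined protocol and SAP*

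**What the plan says.** The Statistical Analysis section is one short paragraph. It states "Power, the probability of rejecting a false null hypothesis, is fixed at 0.90" and then "Two-sided significance level is set at 0.05. The sample size required for an attrition rate of 30% is therefore 40 subjects". The model is given as "A two way-repeated measures ANOVA will be used with main factors of prosthetic used and repeated testing session". The paragraph names no outcome, effect size or standard deviation.

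Section 3 gives a central hypothesis, that the C-leg "will significantly increase everyday function, social interaction, and quality of life in K2 Dysvascular subjects with transfemoral amputation", followed by six numbered hypotheses, each worded as a significant gain over the mechanical knee. Several carry more than one outcome. Hypothesis 2 includes "increased gait speed and distance measured by Six Minute Walk Test (6MWT" alongside step count and the AMP. Hypothesis 3 has four sub-hypotheses. Hypothesis 5 says the C-leg "will significantly improve both static and dynamic balance as measured by Single Leg Stance (SLS), Timed Up and Go (TUG" and three further tests.

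Two sentences come nearest to a ranking. Section 2 says "The study will specifically evaluate the potential of microprocessor knees to improve the quality of life in dysvascular transfemoral amputees". Section 3 says "The study will primarily aim to study the impact of the C-leg on ADLs and community interaction". Both name domains. Neither selects an outcome, and sections 3 and 4 tie no measure to quality of life by name.

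**The concern.** The plan does not say which result would support its central hypothesis. Several rules fit the text: any one significant outcome, one per hypothesis, or all of them. These rules have very different chances of a false claim and of a true one, and nothing stops the choice being made after the results are known. The Discussion of Next Steps section expects the study to establish efficacy in K2 patients, so the intended conclusion is confirmatory and needs a decision rule.

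The 0.90 power has the same gap on a smaller scale. A power figure describes one test against one effect, and the plan identifies neither.

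**Working it through.** **1. Number of outcomes (section 3, including the sub-hypotheses).**

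| Hypothesis | Outcomes | Count |
|---|---|---|
| 1 | GPS-tracked activity | 1 |
| 2 | Step monitor, 6MWT, AMP | 3 |
| 3 | 3a to 3d | 4 |
| 4 | CPI | 1 |
| 5 | SLS, TUG, BBS, FSST, dual-task TUG | 5 |
| 6 | FES, PEQ | 2 |

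Total 1 + 3 + 4 + 1 + 5 + 2 = 16. It is 17 if 6MWT speed and distance are separate, and 15 if the GPS measures in Hypothesis 1 and 3a are the same. Gait aid (3d) is counted, although section 4 describes no measure for it.

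**2. The plan's own figure.** The 40 cannot be reproduced, because no effect or standard deviation is given. Only the attrition step can be checked: 40 × 0.70 = 28 completers, and 28 / 0.70 = 40. That step is consistent.

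**3. Any significant outcome counts.** A two-sided 0.05 test of a device with no effect shows a false benefit with probability 0.05 / 2 = 0.025. For k independent tests the chance of at least one is 1 − 0.975^k. For correlated outcomes I used equicorrelated normal test statistics with numerical integration. The documents give no correlations, so these are assumptions. All nulls are taken as true.

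| k | ρ = 0.9 | ρ = 0.7 | ρ = 0.3 | Independent |
|---|---|---|---|---|
| 15 | 7% | 13% | 23% | 1 − 0.975^15 = 32% |
| 16 | 7% | 13% | 24% | 1 − 0.975^16 = 33% |
| 17 | 7% | 14% | 25% | 1 − 0.975^17 = 35% |

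With only one test per hypothesis (k = 6) the range is 8-12% at ρ from 0.7 to 0.3, and 14% if independent.

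**4. All must succeed.** The chance of a false claim is no greater than for a single test. If each test has 0.90 power, joint power under independence is 0.90^k.

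| k | Independent | ρ = 0.3 | ρ = 0.7 |
|---|---|---|---|
| 6 | 0.90^6 = 53% | 62% | 74% |
| 16 | 0.90^16 = 19% | 40% | 64% |

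**5. What 28 completers can detect on one outcome.** The design is a crossover, so the relevant test is paired, with one value or one period mean per knee. The noncentrality is d × √28 on 27 degrees of freedom at two-sided 0.05, where d is the mean difference divided by the standard deviation of the paired differences.

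- 90% power: d = 0.636, about 0.64 (0.637 on 26 degrees of freedom, with a period or sequence term)
- d = 0.5: power 72%
- d = 0.4: power 53%

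For a balanced two-way repeated measures ANOVA, the knee main effect equals the square of this paired t on period means. The figures therefore describe the planned knee term, provided the standard deviation is that of the value actually analysed.

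**The case against.** The strongest reply has four parts.

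- *The level is per test.* A reader might infer that six hypotheses share a single 0.05. The documents do not say so. The natural reading is 0.05 for each test, which leaves every individual error rate well defined. This stands, and it limits the problem to the central claim.
- *There is a ranking.* A reader might call the hypotheses wholly unranked. Section 3 does put activities of daily living and community interaction first. That also stands, but those domains reach across several hypotheses and many measures, so the ranking does not identify a deciding test.
- *The central hypothesis reads as a conjunction.* It joins function, social interaction and quality of life, so the any-outcome reading is not the one the wording most suggests. This is fair, and it is why inflated error cannot simply be asserted. But a conjunction of domains is not a decision rule. It does not say how many measures per domain must succeed, or which measure stands for quality of life. On the joint reading the cost moves to power.
- *Independence is unrealistic, and familywise control in a single-site study of 40 is debatable.* TUG, dual-task TUG, BBS and FSST are related balance tests in the same people, so the 33% is an upper marker and the correlated range is the fairer guide. Formal adjustment of secondary outcomes is a choice. Naming what decides the central claim is not.

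**Conclusion.** The concern holds for the missing primary outcome and success rule, which must be fixed before outcome data are seen. The error rate of the central claim is undefined, which is not the same as inflated. Over 16 outcomes, an any-outcome rule gives a false-benefit chance of about 13-24% (correlations 0.7 to 0.3; 7% at 0.9) against 2.5% for one test. An all-outcomes rule gives joint power of about 40-64% (correlations 0.3 to 0.7). These sizes rest on assumed equal correlations. The first also assumes no true effect on any outcome, and the second assumes 0.90 power on each.

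The unattached 0.90 is a secondary reporting gap. A reader might infer that 40 is too few. The documents do not support that: the size cannot be verified without an effect, and the one checkable step, 28 to 40, agrees.

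**What to change.** Before outcome data are seen:

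1. Name one primary outcome that is already scheduled in the assessment period and fits the section 3 aim, with its metric and time window. The Data Collection and Analysis section explicitly places the AMP, the 6MWT and GPS over the last two weeks in that period; the sponsor chooses. The deciding test is the within-subject C-leg versus mechanical-knee contrast at two-sided 0.05, over assessment-period visits only. Baseline and acclimation visits are excluded, because the Study Design table also shows monthly collection during acclimation. State that support for the central hypothesis is judged on this outcome, and word the conclusion for its domain.
2. Label all other outcomes secondary or exploratory, with no confirmatory claim. If confirmatory secondary claims are wanted, a Holm procedure applied only after a significant primary result is an option.
3. Restate the power sentence for the primary outcome only, as a description of what the fixed size can detect and not as its justification. For example: 40 randomised with 30% attrition leave 28 completers, who give 90% power at two-sided 0.05 for a mean within-subject difference of about 0.64 SD of the paired differences (72% at 0.5, 53% at 0.4). Define that SD on the value analysed, give the difference in the outcome's own units, and cite the source of the SD.

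If the primary outcome comes from the three measures named in step 1, no extra subjects, visits or measures are needed. The cost is a narrower central conclusion, weaker secondary claims and a less favourable power statement.

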# 4) Research Methods: Study Design:

The study will have a randomized, repeated measures design. Due to the high rate of attrition we will randomize a total of 40 subjects, 20 into each of the groups below.

Group I

Mech Knee+Old Foot	C-leg + New Foot	C-Leg + New Foot	Mech knee + New Foot	Mech knee + New Foot
>6 months post TF prosthetic fitting	Acclimation	Assessment	Acclimation	Assessment
Duration	3 months	3 months	3 months	3 months
Data Collection	Monthly	Monthly	Monthly	Monthly

Group II

Mech Knee+Old Foot	Mech Knee + New Foot	Mech Knee +New Foot	C-Leg+ New Foot	C-Leg+ New Foot
>6 months post TF prosthetic fitting	Acclimation	Assessment	Acclimation	Assessment
Duration	3 months	3 months	3 months	3 months
Data Collection	Monthly	Monthly	Monthly	Monthly

All measures will be administered and data collected under the supervision of a licensed physical therapist.

- I. Assess and compare mobility in TF amputees:
  - a. To quantify community ambulation including time spent out of the home, use of public transport, GPS technology will be used. Subjects will be required to wear a GPS monitor on their belts during the day. This will track their activities in their homes and in the community.
  - b. To assess functional mobility the Amputee Mobility Predictor will be used. A standardized sequence of mobility tests with the prosthesis will be administered on the first pre-acclimation session. The patient will be scored out of 39.
  - c. To quantify fall risk and functional mobility the Timed Up and Go (TUG) test will be used. TUG is the time taken for the subject to get up from chair, walk 3 meters and sits down; measured in seconds.
  - d. To objectify the amount of steps in ADLs and functional mobility the Step Activity Monitor will be used. The subject will be given a monitor that he/she will have to wear around his/her ankle. This will record the number of steps.
  - e. To determine community and social participation, the Community Participation Indicators questionnaire will be used. It is a valid, new generation of self-report outcome measure for community participation. It will take 15-30 minutes to complete and will be administered in room 1771.
- II. Assess and compare gait distance and speed:

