# **Data Collection and Analysis**

Subjects will be screened and medical history and information relevant to why and when they received an amputation will be accessed from their medical records. Subjects will be explained the study design, procedures, tests, questionnaires and physical therapy visits asked to sign an informed consent prior to participating in the study. After subjects are randomized into two groups, they will be provided with a GPS device and a step activity monitor which will track their walking/mobility patterns at home and in the community for 4 weeks. When they return, over 1-2 visits, they will be assessed for a full battery of baseline outcome measures: six minute walk test (6 mwt), Amputee Mobility Predictor (AMP), Timed Up and GO (TUG), BERG balance test,. They will also be required to fill in self-report questionnaires for falls and the PEQ. They will then be fitted with the randomized prosthesis and new foot by a certified prosthetist. There will a period of acclimation for 3 months during which patients will be provided physical therapy with either the C-leg with a new foot or a mechanical leg with a new foot. Subjects will come for an average of two times a week for physical therapy training. The pre-training visits will include 1 for informed consent and GPS, 1-2 for evaluation and an additional 1-2 for prosthetic fit. The training sessions will be a maximum of 14. There will also be 1-2 reassessment visits. This will be repeated for the other prosthesis. There will be a maximum total of up to 45 visits. Subjects will be compensated \$40 per session for evaluation and assessments, prosthetic fittings and training sessions. This is the usual amount in similar studies and other studies at the Rehabilitation Institute of Chicago. The total compensation will be determined by the number of sessions that the subject completes while enrolled in the study. There will be 2 sessions allowed for a subject to be paid, even if they arrive but are unable to complete a session due to unscheduled issues (such as illness). However, if patients miss 3 or more consecutive visits, or experience a medical illness that may/may not require hospitalization, patients may have to be withdrawn from the study. Patients will be offered the additional service of adjustments for prosthesis/refining home exercise program in phone or in person, but they will not be compensated for these patient initiated services.

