The training will focus on providing both groups 1) strength training for upper limbs, core and lower limbs, 2) functional training, e.g. sit – stand, gait training on level surfaces, community ambulation and 3) cardiovascular and endurance training. The following 3 months there will be an assessment period for that particular knee and foot combination. In the course of the assessment period, patients will come in at regular intervals for data collection for the AMP and the 6 mwt. During the last 2 weeks of the assessment, patients will be given GPS devices for tracking their mobility data. At the end of 6 months there will be a crossover where patients with the mechanical leg will receive a new C leg + new foot and patients with the C leg will receive a mechanical leg + new foot. Once again, this will be followed by baseline testing, a period of 3 months acclimation with physical therapy sessions and a 3 month period of assessment where patients will come in for data collection. In the last 2 weeks, GPS data will be collected. The data collected will be analyzed for differences in outcome measures caused by the different prosthetic devices.

During the data collection process and the training sessions, a licensed physical therapist will be present to provide supervision and monitoring of the patient's vitals, signs and symptoms. During the sessions, subjects may be photographed or videotaped performing assessments, functional tasks, or exercising, with their consent. The photos and video recordings will not include the subjects face and if used for presentations or publications, will not identify the subject. The data collection and the training sessions will be terminated if the subjects expresses that he/she is unable/does not wish to participate. Subjects will be compensated \$40 per session. Payment will be in cash or by ClinCard per session, at the end of each session. RIC is moving away from using petty cash. During this transition period the subject may be paid in cash or by ClinCard. If a ClinCard is available when you come for the the study, you will be paid by card. If a ClinCard is not available, then you will receive cash payments.

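### The planned ANOVA has no period term for a two-period crossover: a shift between periods costs power, and it moves the knee estimate when completers differ by sequence

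*Combined protocol and SAP*

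**What the plan says.** Study Design describes the trial in these words: "The study will have a randomized, repeated measures design". Its two group tables show 20 subjects starting on the C-Leg and 20 on the mechanical knee. Each knee has a 3-month acclimation and a 3-month assessment. Data Collection and Analysis confirms the switch: "At the end of 6 months there will be a crossover where patients with the mechanical leg will receive a new C leg". It describes physical therapy with the first prosthesis and adds: "This will be repeated for the other prosthesis".

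Statistical Analysis holds the only analysis model: "A two way-repeated measures ANOVA will be used with main factors of prosthetic used and repeated testing session". Neither period nor sequence is named anywhere as an analysis term, and session is not defined.

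Outcomes follow different schedules. During the assessment phase, "patients will come in at regular intervals for data collection for the AMP and the 6 mwt". For GPS, the plan is "During the last 2 weeks of the assessment, patients will be given GPS devices for tracking their mobility data". The Study Design tables show monthly collection throughout.

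**The concern.** Subjects train and are tested in both periods, so outcomes in the second period may differ from those in the first whichever knee is worn. A crossover analysis normally removes such a shift with a period term. Without one, the shift adds to subjects' C-Leg-minus-mechanical differences in one sequence and subtracts from them in the other.

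Two things are at stake. With equal completers the knee estimate is unbiased, but the error term is too large and power falls below the planned 90%. With unequal completers the knee estimate itself moves, in a direction set by which sequence lost more subjects. The plan expects 30% attrition, so unequal completers are likely.

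The stated model also does not fit every outcome. GPS yields one post-acclimation value per knee, so there is no session factor to fit, and the ANOVA reduces to a paired test.

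**Working it through.** **Inputs from the documents.** 40 randomised, 20 per sequence, 30% attrition; "Two-sided significance level is set at 0.05"; "Power, the probability of rejecting a false null hypothesis, is fixed at 0.90".

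**The plan's own figure.** 40 × (1 − 0.30) = 28 completers, and 28 / 0.70 = 40, so the attrition step reproduces. The 90% power cannot be reproduced, because no effect size, SD or primary outcome is given. Back-solving with a paired t test, 28 completers have 90% power for 0.636 SD of the within-subject knee difference (SDd). That value is used below as an assumption.

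**What session can mean.** A two-way repeated-measures ANOVA crosses knee with session within subject, so each subject must fill every knee-by-session cell. If sessions were numbered through the whole study, half of each subject's cells would be empty. Session is therefore the visit within a knee's phase. The knee test is then a one-sample t test on each subject's difference D; on a simulated data set the ANOVA F for knee equalled t squared (13.57).

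**Model.** Let τ be the knee effect and p the shift from period 1 to period 2, both in SDd, with n1 C-Leg-first and n2 mechanical-first completers.

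- C-Leg first: D has mean τ − p.
- Mechanical first: D has mean τ + p.
- Shift in the estimate without a period term: p × (n2 − n1) / (n1 + n2).
- Standard error inflation at 14/14: √(1 + p² × 28/27).
- With a period term: no shift, SE = 0.5 × √(1/n1 + 1/n2), with n − 2 degrees of freedom.

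**Equal completers (14/14).** At p = 0.5 the inflation is √(1 + 0.25 × 28/27) = 1.12. Power and type I error are simulated, with 200,000 trials per setting.

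| p (SDd) | SE too large by | Type I error | Power as planned | Power with period |
|---|---|---|---|---|
| 0 | 0% | 5.0% | 90.0% | 89.9% |
| 0.25 | 3% | about 4.3% | 89% | 89.9% |
| 0.5 | 12% | about 2.9% | 85% | 89.9% |
| 1.0 | 43% | 0.6% | 67% | 89.9% |

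**Unequal completers, p = 0.5.** For 17/11 the shift is 0.5 × (11 − 17) / 28 = −0.11.

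| C-Leg-first / mechanical-first | Shift in estimate (SDd) | Power as planned | Power with period |
|---|---|---|---|
| 15/13 | −0.04 | 80% | 89.8% |
| 13/15 | +0.04 | 89% | 89.8% |
| 17/11 | −0.11 | 69% | 88.5% |
| 11/17 | +0.11 | 94% | 88.5% |

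The 94% is bias, not a gain. If p is negative, the signs reverse.

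**How likely is imbalance?** Suppose exactly 28 of 40 complete and loss is unrelated to sequence. The chance of an equal split is C(20,14)² / C(40,28) = 27%. A gap of 2 has probability 43%, a gap of 4 or more 30%, and a gap of 6 or more 8%. If each subject instead drops out independently with probability 30%, a gap of 4 or more has probability 23%. Averaged over the fixed-28 splits, power at p = 0.25, 0.5 and 1.0 is 89%, 84% and 65%, against 89.6% with a period term. Type I error is 4.6%, 3.5% and 1.5%.

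**The case against.** The strongest objection is that session is undefined, so it might be numbered through the whole study. Fitted as a factor in a linear model with subject effects, that coding does absorb the shift. With 18/10 completers, a true knee effect of 0 and a shift of 1 outcome unit, the knee estimate averages −0.30 when sessions are numbered within phase and about −0.01 when numbered through the study. But that is a different model from the crossed ANOVA the plan names, and nothing in the plan points to it. It strengthens the case for defining the term.

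The second objection is that the size of harm is assumed. This stands. The documents give neither the size nor the sign of any shift. At 0.25 SDd with equal completers the loss is about one point of power. A shift of 1.0 SDd exceeds the assumed treatment effect and should be read as an outer bound.

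Third, false-positive risk is small. This also largely stands. At p = 0.5 the type I error is below 5% up to a 16/12 split, about 5.5% at 17/11 and 7.7% at 18/10. A split of 18/10 or worse has about 1.4% probability under the fixed-28 calculation. The main harm is lost power and an estimate that depends on who drops out.

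Finally, a period term does not address carryover, and the plan is silent on subjects who complete only one period and on how baseline measurements enter. Those are separate gaps and do not weaken this point.

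**Conclusion.** The concern holds and should be fixed. The plan describes a two-period crossover and analyses it without period. That much follows from the text and from how a knee-by-session repeated-measures ANOVA works.

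The size of the harm is conditional. It rests on 28 completers, an effect of 0.636 SDd and an assumed shift. On those terms the loss with equal completers runs from about 1 point of power at a shift of 0.25 SDd to about 5 at 0.5 and about 23 at 1.0. The movement of the knee estimate averages to zero if loss is unrelated to sequence, although any single trial can still be off by the amounts shown. It becomes systematic only if loss differs by sequence.

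**What to change.** Replace the ANOVA sentence with wording such as: *For each outcome, assessment-phase values in each period will be averaged to one value per subject per period (for GPS, the single window in the last 2 weeks). These will be analysed with a linear mixed model with fixed effects for knee, period and sequence and a random subject effect; the knee effect is the test.*

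Period is the term that corrects; sequence alone does not change the within-subject knee contrast. With complete data this equals a two-sample t test between the groups on each subject's period-1-minus-period-2 value. The group means are τ − p and −τ − p, so half their difference is τ. That test is a fallback if the software the plan names cannot fit the mixed model.

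Define session as the visit within an assessment phase. Use session and knee-by-session only in a secondary model for outcomes measured repeatedly in that phase, and include a subject-by-period random effect. This matters: with a random subject effect alone, simulated visit-level data (three visits per phase, 14/14, no knee effect, p = 0.5) gave a type I error of about 12% to 22% when 20% to 50% of within-subject variance was shared by the visits of a phase.

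The change is to wording only, since period and sequence are known for every subject. It costs one degree of freedom plus a small loss when completers are unequal. If there is no period shift, power goes from 90.0% to 89.9% at 14/14, 89.8% at 15/13, 89.3% at 16/12 and 88.5% at 17/11.

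### The knee-by-session ANOVA has no period or sequence term and no missing-value rule; a crossover analysis of all collected values would protect outcomes measured repeatedly on each knee.

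*Combined protocol and SAP*

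**What the plan says.** The Statistical Analysis section names one method: "A two way-repeated measures ANOVA will be used with main factors of prosthetic used and repeated testing session". It fixes power at 0.90 and two-sided significance at 0.05, and then states: "The sample size required for an attrition rate of 30% is therefore 40 subjects to be randomized into 2 groups of 20 each". On software it says "Statview version 5.0.1 will be used for statistical analysis". Neither this section nor any other says what happens to missing values, which subjects are analysed, or whether data from withdrawn subjects are used.

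The design is a crossover. Data Collection and Analysis says "At the end of 6 months there will be a crossover", after which each group changes to the other knee.

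The visit schedule is described in several ways:

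- The table under Research Methods: Study Design shows monthly collection in every 3-month block, acclimation as well as assessment.
- Data Collection and Analysis says of the visits for one prosthesis, "There will also be 1-2 reassessment visits".
- The same section says that during assessment "patients will come in at regular intervals for data collection for the AMP and the 6 mwt".
- For the AMP, the Study Design section says instead: "A standardized sequence of mobility tests with the prosthesis will be administered on the first pre-acclimation session".
- For GPS: "During the last 2 weeks of the assessment, patients will be given GPS devices for tracking their mobility data". The same applies after the crossover, so follow-up GPS yields about one value per knee.

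The Withdrawal criteria remove a subject at three missed sessions in a row or five in all on one leg. A subject with fewer misses stays in.

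**The concern.** A classical two-way repeated-measures ANOVA needs a full row of knee-by-session values for each subject. If one visit is missed, the subject's other visits are lost for that outcome too. The 30% allowance is given for attrition, and the plan does not say whether it also covers retained subjects with a gap. If it does not, the usable number could fall below the number the power statement relies on. With no rule stated, the handling of gaps would be settled after the data are seen.

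The missing period term is a second weakness. Without it, any change between the two halves of the trial (training, practice, disease progression) is mixed into the knee comparison once withdrawals leave the two sequences unequal.

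**Working it through.** **Inputs from the plan.** 40 randomised, 20 per sequence; 30% attrition; power 0.90; two-sided 0.05. **Assumed, because the plan does not give them:** effect size, missed-visit rate q, clustering of misses, and listwise deletion.

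**The plan's own figure.** 40 x 0.70 = 28 completers, and 28 / 0.70 = 40, so the attrition step is consistent. The 28 cannot be verified, since no effect size, SD or sizing outcome is given. Back-solving the paired noncentral-t power for 0.90 at n = 28 gives an effect of 0.636 SD of the paired difference (0.899 with one degree of freedom spent on period).

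**Cells per outcome.** One visit per knee gives 2 cells, and two give 4 (the 1-2 reassessment visits). Monthly in the assessment block only gives 2 x 3 = 6. Monthly in both blocks gives 2 x 6 = 12.

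**Complete-case power, independent misses.** The chance of a complete row with k cells is (1 - q)^k. Power is averaged over a binomial number of complete subjects out of those retained. At q = 5%, the expected complete subjects out of 28 are 28 x 0.95^2 = 25.3, 28 x 0.95^4 = 22.8 and 28 x 0.95^6 = 20.6.

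| Retained | Cells | 2% missed | 5% missed | 10% missed |
|---|---|---|---|---|
| 28 | 2 | 0.89 | 0.86 | 0.82 |
| 28 | 4 | 0.87 | 0.82 | 0.72 |
| 28 | 6 | 0.86 | 0.78 | 0.62 |
| 32 | 2 | 0.93 | 0.91 | 0.87 |
| 32 | 4 | 0.91 | 0.87 | 0.79 |
| 32 | 6 | 0.90 | 0.83 | 0.68 |

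With 12 cells and 28 retained, 5% missed gives about 0.63. With 32 retained, power stays at 0.90 or above until missed visits exceed about 6.2%, 3.1% or 2.1% (2, 4, 6 cells).

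**Clustered misses.** Take a beta-binomial with within-subject correlation 0.4, so a + b = (1 - 0.4)/0.4 = 1.5 and b = 0.95 x 1.5 = 1.425. The chance of a complete row is the product of (1.425 + j)/(1.5 + j) for j = 0 to k - 1, which is 0.922, 0.887 and 0.864 for 2, 4 and 6 cells. Power with 28 retained is then 0.87, 0.86 and 0.85. At 10% missed and 6 cells it is 0.78 rather than 0.62.

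**Effect-size range** (28 retained, 4 cells, 5% missed, independent): 0.78 at 0.6 SD (0.86 with none missing); 0.95 at 0.8 SD (0.98 with none missing).

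**What the remedies recover.** Simulation with 28 retained subjects, a period effect and a session trend, 4,000 trials per setting; ranges are over two assumed levels of visit noise (one level for 2 cells):

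| Cells | Missed | Complete case | Mean of available visits | Mixed model |
|---|---|---|---|---|
| 2 | 5% | 0.87 | 0.87 | 0.87 |
| 2 | 10% | 0.81 | 0.81 | 0.83 |
| 4 | 5% | 0.82 | 0.89 | 0.89-0.90 |
| 4 | 10% | 0.70-0.71 | 0.86-0.88 | 0.87-0.88 |
| 6 | 5% | 0.76-0.77 | 0.89-0.90 | 0.90 |
| 6 | 10% | 0.60 | 0.86-0.89 | 0.87-0.89 |

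For 4 and 6 cells the two remedies differ by at most 0.006. Type I error of the mixed model was 0.047 to 0.051.

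A second simulation (600 runs per setting) kept all 40 randomised subjects, with 30% dropout at a uniformly chosen session and three visits per knee. At 5% missed, the complete-case ANOVA had power 0.76-0.81 and the mixed model 0.92. At 10% they had 0.58-0.64 and 0.91-0.93. With dropout alone they had 0.89-0.91 and 0.94-0.95.

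**Period.** Let n1 subjects complete with the C-leg first and n2 with it second, and let p be the change from period 1 to period 2. The unadjusted knee difference is biased by p x (n2 - n1)/(n1 + n2). This is zero at 14 and 14, and nonzero once withdrawals differ between the sequences.

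**The case against.** The loss depends on a chain of assumptions: listwise deletion, 28 being exactly the number needed, 12 of 40 actually withdrawing, and an assumed rate of independent misses. Relaxing any one of them shrinks it. This stands, and it is why the figures are only an illustration. A reader might infer that the trial is underpowered. The documents do not support that, because they give no effect size, SD or missed-visit rate and do not say that incomplete subjects are dropped.

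The withdrawal rule is weak evidence that outcome values will be missing. It counts sessions, and up to 14 per knee are training sessions whose loss costs no outcome value. Nothing bars rescheduling an assessment, and hospitalisation leads to withdrawal, which the attrition allowance is meant to cover. This also stands: the rule permits gaps but does not predict them.

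The scope is narrow. The 6MWT is clearly repeated, and the AMP only if the Data Collection text governs over the Study Design text. Hypotheses 1 and 3 rest on GPS, where the gain is about 0.00 to 0.02. This stands.

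A reader might also infer that a mixed model is required. The simulations do not support that, since averaging the available visits recovers nearly all the power. The mixed model's further advantage is its use of partial data from withdrawn subjects.

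None of this removes the core point: the one analysis named omits the crossover structure and leaves missing data to an unstated rule.

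**Conclusion.** The concern holds in limited form and should be addressed, with medium confidence in its size. That the plan has no period or sequence term and no missing-value rule can be read directly from the text. How much power is lost cannot be. With 28 retained, 5% of visits missed and complete-case analysis, the loss from 0.90 is about 4, 8 or 12 points for 2, 4 or 6 cells if misses are independent, and about 3, 4 or 5 points if they cluster at correlation 0.4. It is larger if monthly acclimation visits also count, and small or absent if fewer subjects withdraw or few visits are missed. The exposure is confined to outcomes repeated on each knee.

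**What to change.** Specify an analysis of all values collected from all randomised subjects, including those before withdrawal, with knee, period and sequence represented. Either form is acceptable:

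- **(a)** Average each subject's available visits on each knee, take the period difference, and compare it between the two sequences with a two-sample t-test. This needs no new software, but only subjects seen on both knees contribute.
- **(b)** Fit a REML linear mixed model with small-sample degrees of freedom: knee, period, sequence and session fixed; subject and subject-by-knee random (subject only where there is one value per knee). This also uses partial data from withdrawn subjects.

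In addition:

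- State the number of outcome visits per knee for each outcome, and whether acclimation values enter the comparison.
- Reconcile the Study Design table, the AMP item below it and the Data Collection and Analysis text on these visits.
- Report withdrawals and hospitalisations by knee worn, so that the missing-at-random assumption can be judged.

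The cost is a change of analysis wording, with no extra subjects or visits. Form (b) may need software other than the package named; the documents do not show whether that package fits such a model. The analysis assumes data are missing at random, which withdrawal for illness may strain. Subjects seen on one knee add little, and outcomes with one value per knee, such as follow-up GPS, gain little.
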